8.4.4 Planned Interim Analyses

No interim analyses are planned given the short duration of enrollment and follow-up.

Subgroup Analyses

Interactions will be evaluated and subgroup analyses conducted to determine whether the effect or lack thereof prevails throughout particular subgroups of participants. The following factors will be considered for subgroup analysis, if there is a significant interaction between the factor of interest and the treatment effect:

- Race/ethnicity
- BMI category (obese vs non-obese)
- Type of labor (labor vs no labor)
- Type of anesthesia
 - General, spinal, combined spinal-epidural, epidural
 - Neuraxial morphine administration
- Skin incisional type (low transverse vs vertical midline)
- Primary vs repeat cesarean

• Time from delivery to discharge (<48 hours, \geq 48 hours).

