2.3.3 Assessment of Potential Risks and Benefits

As described above, potential risks are not more than encountered in usual care after cesarean delivery. Treatment with the TrueRelief device may improve pain control and reduce opioid requirements.

3. Study Design

This is a blinded randomized trial of 134 individuals undergoing a cesarean delivery who are randomized after cesarean to three times use of non-invasive bioelectronic treatment with TrueRelief device or identical appearing sham device for post-cesarean pain management.

The primary endpoint is the total inpatient morphine milligram equivalents used during hospital admission. The primary hypothesis is that three times use of non-invasive bioelectronic treatment with TrueRelief device decreases the total inpatient morphine milligram equivalents used during hospital admission compared to use with identical appearing sham device. Consenting women will be assigned in a 1:1 ratio to one of the two arms using a secure internet based randomization system. Individuals will be followed through 6 weeks postpartum.

4. Objectives and Endpoints

OBJECTIVES	ENDPOINTS		
Primary			
To evaluate whether non-invasive bioelectronic treatment reduces inpatient post-cesarean opioid consumption.	Total inpatient postoperative opioid consumption in morphine milligram equivalents (MME).		
Secondary			
To evaluate whether non-invasive bioelectronic treatment post-cesarean decreases opioid refill prescriptions.	Opioid prescription filled (beyond that prescribed at discharge) between discharge and six weeks postpartum.		
	Total number of opioid prescriptions filled by six weeks postpartum (beyond that prescribed at discharge).		
To evaluate whether non-invasive bioelectronic treatment post-cesarean decreases the total amount of opioid tablets prescribed at discharge.	Number of opioid tablets prescribed at discharge.		
To evaluate whether non-invasive bioelectronic treatment post-cesarean reduces pain intensity pain scores	Pain severity scores (worst, least, average, current) in last 24 hours assessed on the Brief Pain Inventory numeric scale from 0 to 10 at discharge		

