5.4 Strategies for Recruitment and Retention

5.4.1Recruitment Plan

Good recruitment will depend on access, promotion, education and clinical staff buy-in. Research staff will view the daily schedule to review who has had a cesarean. If eligible by medical record review, research staff will approach participants preoperatively or post-operative day 0 to inform them about the study. Randomization should occur on postoperative day 0, but not earlier.

Care providers will be educated about the study via targeted information sessions. It has been found to be helpful to provide in-person informative sessions with specific groups of providers, for example faculty, residents and fellows.

The Ohio State Wexner Medical Center is a large academic medical center with over 5000 deliveries per year. Assuming a 30% rate of cesarean deliveries this is approximately 1500 cesarean deliveries per year. Not every day has 24/7 coverage; therefore it is conservatively assumed that approximately 4 individuals daily are potentially available to enroll on a weekday. It is expected that the number of women who meet the exclusion criteria will be less than 1 percent. Even if 20% of physicians are reluctant to allow their patients to participate (relevant in the setting of private physician deliveries within a hospital) and 60% of women refuse consent for the trial, over 360 women could be enrolled annually.

We are currently conducting a randomized trial in women undergoing cesarean delivery. The aim of the trial is to determine whether an individualized opioid prescription protocol (IOPP) at discharge after cesarean delivery is non-inferior to a prescription for a fixed amount of opioid tablets which approximates current standard of care has similar pain control.

Women are randomized after cesarean delivery and research staff has to be present on day of discharge for randomization. Even with these major barriers to recruitment, sites have been able to recruit approximately 24 participants/ month. While these barriers do not apply to this trial, this study does require a medically trained individual to administer the intervention. Thus the study should conservatively be able to enroll at least 24 participants per month.

6. Study Intervention

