6.1 Study Intervention Administration

6.1.1 Study Intervention Description

Women will be randomized on post-operative day 0 to receive treatments with non-invasive bioelectrical device or identical appearing sham device. Three treatments will be given to each patient. The first treatment should be given as soon as is practical after the cesarean section and not longer than two hours after the procedure. The second treatment will be administered 12 hours after the first treatment, but can be given within a range of 10-14 hours after the first treatment to avoid having to wake the patient when sleeping or otherwise disrupt other care being given to the patient. The third and final treatment will be administered 12 hours after the second treatment, but can be given within a range of 10-14 hours after the second treatment, but can be given within a range of 10-14 hours after the second treatment, but can be given within a range of 10-14 hours after the second treatment, but can be given within a range of 10-14 hours after the second treatment, but can be given within a range of 10-14 hours after the second treatment, but can be given within a range of 10-14 hours after the second treatment to avoid having to wake the patient when sleeping or otherwise disrupt other care being given to the patient when sleeping or otherwise disrupt other care being given to the patient.

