8.4.3 Baseline Descriptive Statistics

Baseline factors will be compared by treatment group. If the treatment groups are found to differ on a key pre-treatment factor known to be a risk factor for the outcome, the statistical analyses will adjust for these differences.

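### Time from delivery to discharge is listed as an effect-modification subgroup, but it is settled only after randomization and treatment and it closes the primary endpoint's window (minor, free to fix)

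*Combined protocol and SAP*

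**What the plan says.** The unnumbered Subgroup Analyses text under Section 8.4.4 plans interaction tests and subgroup analyses to see whether the treatment effect holds across groups of participants. The last factor listed is "Time from delivery to discharge (<48 hours" against 48 hours or more). A factor is taken up "if there is a significant interaction between the factor of interest and the treatment effect". The other factors are race/ethnicity, BMI category, labor, anesthesia and neuraxial morphine, skin incision, and primary or repeat cesarean.

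Four other places bear on this one:

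- **Randomization.** Section 3 describes individuals "who are randomized after cesarean to three times use" of the device or sham, and Section 5.4.1 adds: "Randomization should occur on postoperative day 0, but not earlier".
- **Treatment.** Section 6.1.1 puts the first treatment "not longer than two hours after the procedure", the second 10 to 14 hours later, and the third "within a range of 10-14 hours after the second treatment". Section 6.1.2 places all three before discharge.
- **Endpoint.** Section 3: "The primary endpoint is the total inpatient morphine milligram equivalents used during hospital admission". The summing therefore stops at discharge, not at a fixed hour.
- **Adjustment.** Section 8.4.3 confines covariate adjustment to a "key pre-treatment factor known to be a risk factor for the outcome". The subgroup text has no matching limit, and nothing labels time to discharge as post-randomization or descriptive.

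**The concern.** A subgroup comparison keeps the protection of randomization only if membership could not have been altered by treatment. Time to discharge fails that condition. A device meant to improve pain control and reduce opioid use might also let some women go home earlier. If so, women cross the 48-hour line in one arm only, and each stratum then compares different kinds of women. Because discharge also ends the accrual of MME, any part of the effect that works through a shorter stay is partly removed by splitting on stay.

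At stake is how one subgroup result is read. A difference between strata, or a lack of one, could be reported as showing where the device works when it reflects who was sorted into each stratum.

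**Working it through.** **1. Order of events.** The latest third treatment on the Section 6.1.1 windows is about 2 + 14 + 14 = 30 h after the procedure, and the earliest about 0 + 10 + 10 = 20 h. Both come before the 48 h cut, so stratum membership is settled after randomization and after all treatment.

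**2. The plan's own figure, for scale.** Section 8.2 gives mean 42 MME, SD 15, a 20% reduction to 33.6 (difference 8.4), 90% power and N = 134. Taking alpha as 0.05 two-sided (Section 8.2 does not state it):

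n per arm = 2 × (1.960 + 1.282)² × 15² / 8.4² = 67.01

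This is 68 per arm if rounded up. Power at 67 per arm is 0.89995 (0.896 by the exact t test), so 134 is reproduced. The concern does not touch it; 8.4 MME serves as the yardstick.

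**3. Illustration A: the device acts only by shortening stay.** The documents give no stay data, so these inputs are assumptions: stay normal with mean 54 h and SD 12 h, truncated below 30 h; MME = hourly rate × stay, scaled to mean 42 and SD 15; rate-stay correlation 0 to 0.5; device stay shorter by 4 h, rate unchanged.

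With correlation 0 it can be done by hand. Truncation raises mean stay to 54.66 h, so the mean rate is 42 / 54.66 = 0.768 MME/h. A treated woman is below 48 h if her stay without the device would have been below 52 h.

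| | Sham | Device | Difference × 0.768 |
|---|---|---|---|
| Share <48 h | 29% | 42% | |
| Mean stay, all | 54.66 h | 50.66 h | -3.07 MME |
| Mean stay, <48 h | 41.48 h | 40.09 h | -1.07 MME |
| Mean stay, ≥48 h | 60.11 h | 58.34 h | -1.36 MME |

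With strata fixed before randomization, the overall effect is a weighted average of the stratum effects. No weighting of -1.07 and -1.36 gives -3.07. The gap arises because women moved between strata in one arm.

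Simulation with 2 million women per arm, at correlations 0 / 0.3 / 0.5:

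| Stay shift | Overall | <48 h | ≥48 h |
|---|---|---|---|
| 2 h | -1.5 / -1.5 / -1.5 | -0.5 / -0.2 / -0.1 | -0.7 / -0.5 / -0.4 |
| 4 h | -3.06 / -3.04 / -3.02 | -1.05 / -0.49 / -0.26 | -1.35 / -0.85 / -0.58 |

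With no shift, all differences are about 0. Across assumed mean stays of 48 to 60 h, the 4 h shift gives -2.7 to -3.4 overall and +0.1 to -1.6 within strata.

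**4. Illustration B: stay shortens but MME is unaffected.** Assumed: stay mean 54 h, SD 8 h, MME-stay correlation r from 0.3 to 0.7. A 4 h shift moves the cut from z = -0.75 (23% below 48 h) to z = -0.25 (40%). The false device-minus-sham differences are:

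- <48 h: 15 × r × (1.329 - 0.964), or +1.6 (r = 0.3) to +3.8 (r = 0.7)
- ≥48 h: 15 × r × (0.646 - 0.389), or +1.2 to +2.7

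Simulation gave +1.6 to +3.9 and +1.1 to +2.7, with an overall difference of about 0. The sign is the reverse of A.

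**5. How often the gate would open.** In case A with a 4 h shift at N = 134, an interaction test at two-sided 5% (10,000 simulated trials) was significant in 2–3% of trials with pooled variance and 5–6% with unequal variance, so about the chance rate or below. The Wilcoxon/Hodges-Lehmann branch of Section 8.4.2 was not modelled.

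**The case against.** The strongest reply is that the bias needs the device to change length of stay. Nothing in the documents says it does, and stay is not an endpoint. That stands: without a change in stay there is no bias, and every stay figure above is an assumption. Since the two illustrations also disagree in sign, neither the size nor the direction is known. Even so, the plan does not list a comparison of stay by arm, so a reader of the subgroup result could not tell which situation applied.

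Second, the significant-interaction gate limits the damage. This also stands as a limit on frequency: in the 4 h case false interactions are not inflated. But the gate does not make the strata comparable once it has opened, nor does a non-significant test on such strata show that the effect is uniform.

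Third, larger absolute effects in longer stays need not be bias. That is correct. With unchanged stay, a uniform 20% cut in the rate of use gives -5.6 to -6.4 MME below 48 h and -9.2 to -9.6 at or above it, both true differences. Such scale dependence would arise with any factor related to MME and is no special fault of this one.

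Fourth, the 30 h figure is soft. Section 6.1.2 words the spacing differently, and Section 9.1.1 allows approach up to 24 hours after delivery. The order of events does not depend on it, since all treatments come before discharge.

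Finally, a look at results by stay has descriptive value when the endpoint window ends at discharge. Agreed, which is why relabelling is an acceptable alternative to deletion.

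**Conclusion.** The concern holds, as a minor point. That time to discharge is a post-randomization variable which also closes the endpoint window follows from the documents alone. That it would distort the stratum results is conditional on the device changing stay. Under the assumptions of illustration A, a 4 h shorter stay leaves only -0.3 to -1.4 MME within strata of an overall effect of about -3.0; under those of B, it creates false differences of +1.1 to +3.9 MME where there is no effect. Against the design difference of 8.4 MME these are modest, and the true size is unknown. The primary comparison of all randomized participants (Section 8.3) and N = 134 are unaffected.

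**What to change.** In the Subgroup Analyses list under Section 8.4.4, do one of the following:

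- delete time from delivery to discharge and state that subgroup factors are limited to those fixed before randomization; or
- keep it under a separate label as a descriptive, post-randomization breakdown that is not a test of effect modification.

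In either case, report length of stay by arm for all randomized participants, so that readers can see whether stay differed.

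This means one line deleted or relabelled and one row added to the tables. Discharge time is already needed for the planned subgroup, so there is no new data collection and no change to the sample size or the primary analysis.

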8.4.7 Tabulation of Individual Participant Data

Participant data will only be reported in aggregate in study abstracts, presentations or manuscripts.

9 Supporting Documentation and Operational Considerations

9.1 Data Regulatory, Ethical, and Study Oversight Considerations

9.1.1 Informed Consent

A single IRB will be used for this study. A HIPAA Waiver of Consent for recruitment purposes will be obtained to allow clinical sites to review electronic medical records to identify potentially eligible participants.

Prior to cesarean delivery or within first 24 hours after cesarean delivery, women will be approached for participation into the study. Full disclosure of the nature and potential risks of participating in the trial is to be made. Women that elect to participate in the study will sign the study consent. The consent form describes in detail the study intervention, study procedures, and risks is given to the participant and written documentation of informed consent is required prior to randomization.

The following consent materials are submitted with this protocol: study consent and assent, participant completed questionnaire..All participant materials will be IRB approved.. Both verbal and written informed consent and authorization will be obtained in the participant's fluent language. Participants not fluent in English will be excluded.

9.1.2 Confidentiality and Privacy

Participant confidentiality and privacy is strictly held in trust by the participating investigators, their staff, and the sponsor(s) and persons or organizations working with the sponsor. All research activities will be conducted in as private a setting as possible. The following individuals and/or agencies will be able to review medical and research records:

• The study doctor, study staff and other medical professionals who may be evaluating the study.

The study participant's contact information will be securely stored at each clinical site for internal use during the study. At the end of the study, all records will continue to be kept in a secure location for as long a period as dictated by the reviewing IRB, Institutional policies, or sponsor requirements.

Additional details are provided in the full study consent form and authorization.

9.1.3 Clinical Monitoring

Clinical monitoring is performed by PI.

9.1.4 Data Handling and Record Keeping

Data will be collected on standardized forms on which nearly all responses have been pre-coded. Data collection is the responsibility of the clinical trial staff at the site under the supervision of the principle investigator. The investigator is responsible for ensuring the accuracy, completeness, legibility, and timeliness of the data reported.

9.1.5 **Protocol Deviations**

A protocol deviation is any noncompliance with the clinical trial protocol, International Conference on Harmonisation Good Clinical Practice (ICH GCP), or Manual of Procedures (MOP) requirements. The noncompliance may be either on the part of the participant, the investigator, or the study site staff. As a result of deviations, corrective actions are to be developed by the site and implemented promptly. A list of protocol deviations that must be submitted to the IRB are included in the manual of procedures.

